#### **9.2.5. Inclusion/exclusion Criteria**

Patients with LVH from undiagnosed etiology and the following inclusion/exclusion criteria:

##### **1. Inclusion Criteria.**

- a. Patient signed informed consent
- b. Males and Females
- c. Age  $\geq 50$  years
- d. Left ventricular hypertrophy (LVH) defined as end-diastolic LV maximum wall thickness (MWT)  $\geq 15$ mm in Echocardiogram.
- e. Plan to undergo or recently underwent radionuclide bone scintigraphy and/or SPECT with any of the following radio labelled tracers:  $^{99m}\text{Tc}$ -DPD or  $^{99m}\text{Tc}$ -PYP or  $^{99m}\text{Tc}$ -HMDP\*.

*\* Scintigraphy will be defined at each site according to the standard grading:*

*Grade 0 = absent cardiac uptake*

*Grade 1 = mild uptake less than bone*

*Grade 2 = moderate uptake equal to bone*

*Grade 3 = high uptake greater than bone*

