## 2. Exclusion Criteria:

- a. Etiological diagnosis explaining the LVH prior to patient inclusion (eg, Sarcomeric HCM, Myeloma, Fabry disease, Sarcoidosis, any type of amyloidosis [AA, AL, TTR\*\*]).
- b. Severe aortic stenosis defined as aortic valve area (AVA) <1.0 cm^2.

*\*\* TTR diagnosis at exclusion criteria: Direct relative (siblings or parents) of a carrier with a known hereditary mutation in the TTR gene or any patient already diagnosed by any of the following: cardiac fixation at the bone scintigraphy, TR mutation at the genetic testing, biopsy with amyloidosis (positive red congo) and positive TTR staining.*

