## 9.3. Variables

Variable	Data source(s)
Patient informed consent date	PATIENT INCLUSION
Patient visit date	PATIENT INCLUSION
Age ≥50 years	PATIENT INCLUSION
LVH Echo demonstrated end-diastolic LV MWT ≥15mm	PATIENT INCLUSION
Maximal end diastolic wall thickness	PATIENT INCLUSION
Sarcomeric HCM (Genetic testing)	PATIENT INCLUSION
Plasma cell dyscrasia	PATIENT INCLUSION
Fabry disease	PATIENT INCLUSION
AL, AA or any other amyloidosis	PATIENT INCLUSION
Severe aortic stenosis (defined as) Maximal aortic velocity >4 m/s or Mean gradient >40 mmHg	PATIENT INCLUSION
Birth date (mm-yyyy)	PATIENT INFORMATION
Gender	PATIENT INFORMATION
Weight	PATIENT INFORMATION
Height	PATIENT INFORMATION
Ethnic Origin	PATIENT INFORMATION
Date	CLINICAL EVALUATION
Diastolic blood pressure	CLINICAL EVALUATION
Systolic blood pressure	CLINICAL EVALUATION
Diagnosed hypertension	CLINICAL EVALUATION
Antihypertensive medication	CLINICAL EVALUATION
Coronary artery disease	CLINICAL EVALUATION
Renal insufficiency	CLINICAL EVALUATION
Diabetes Mellitus	CLINICAL EVALUATION
Lumbar spinal stenosis 1	CLINICAL EVALUATION
CTS – surgery history 2	CLINICAL EVALUATION
New York heart Association (NYHA) class	CLINICAL EVALUATION
Atrial Fibrillation (AF)	CLINICAL EVALUATION

Variable	Data source(s)
Pacemaker	CLINICAL EVALUATION
AICD (Automatic Implantable Cardiac Defibrillator)	CLINICAL EVALUATION
LGE (Late Gadolinium Enhancement)	CLINICAL EVALUATION
Heart rate	CLINICAL EVALUATION
Sinus rhythm	CLINICAL EVALUATION
PR Interval	CLINICAL EVALUATION
QRS interval	CLINICAL EVALUATION
Sokolow index	CLINICAL EVALUATION
Pseudo-MI pattern	CLINICAL EVALUATION
Poor precordial R wave progression	CLINICAL EVALUATION
LBBB RBBB Paced Intraventricular conduct delay	CLINICAL EVALUATION
Left Ventricular Ejection Fraction (LVEF)	CLINICAL EVALUATION
Left Ventricular Obstruction Tract (LVOT)	CLINICAL EVALUATION
Longitudinal strain done?	CLINICAL EVALUATION
LV end-diastolic diameter	CLINICAL EVALUATION
MWT	CLINICAL EVALUATION
MWT at septum	CLINICAL EVALUATION
MWT posterior wall	CLINICAL EVALUATION
Hypertrophic pattern Apical, Concentric, Asymmetric, Mix	CLINICAL EVALUATION
LV mass index	CLINICAL EVALUATION

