Aortic valvular stenosis	CLINICAL EVALUATION
Pericardial effusion	CLINICAL EVALUATION
Patient scintigraphy date	SCINTIGRAPHY
99mTc-DPD, 99mTc-PYP, 99mTc-HMDP	SCINTIGRAPHY
Grade 0=absent cardiac uptake Grade 1=mild uptake less than bone Grade 2=moderate uptake equal to bone Grade 3=high uptake greater than bone	SCINTIGRAPHY
Walking ability: No Impairment, Impaired but ability to walk without a stick or crutches, Walking only with the help of one stick or crutch, Walking with the help of two sticks or crutches, Confined to a wheelchair or bedridden	ATTR RED FLAGS
SPECT date	SPECT
SPECT Result	SPECT
Paresthesia / Numbness / Sensory loss *	ATTR RED FLAGS
Pain*	ATTR RED FLAGS
Temperature sensory loss*	ATTR RED FLAGS
Muscle weakness*	ATTR RED FLAGS
Carpal tunnel syndrome symptoms	ATTR RED FLAGS
Erectile dysfunction / Vaginal dryness	ATTR RED FLAGS
Orthostatic / postural hypotension (dizziness, syncope)	ATTR RED FLAGS
Urinary difficulties (i.e. dysuria, incontinence...)	ATTR RED FLAGS
Sweating abnormalities	ATTR RED FLAGS
Digestive dysautonomia: Constipation, alternating constipation and diarrhoea, nausea, vomiting...	ATTR RED FLAGS
Early satiety / Gastro paresis	ATTR RED FLAGS
Unintentional weight loss	ATTR RED FLAGS
Visual disturbances: Dry eye / Glaucoma	ATTR RED FLAGS
Creatinine	CLINICAL LABORATORIES
Haemoglobin	CLINICAL LABORATORIES

Variable	Data source(s)
BNP	CLINICAL LABORATORIES
NTproBNP	CLINICAL LABORATORIES
Troponin I	CLINICAL LABORATORIES
Troponin T	CLINICAL LABORATORIES
IFE of serum	CLINICAL LABORATORIES
IFE of urine	CLINICAL LABORATORIES
*sFLC assay	CLINICAL LABORATORIES
Electrophoresis performed?	CLINICAL LABORATORIES
Date	TTR gene sequencing
Result	TTR gene sequencing

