### **9.9.2. Patient Selection**

This constitutes another potential selection bias classically associated with studies. Voluntary or involuntary selection of patients in a study by investigators is inevitable, but this bias can be limited by systematic attempts to enroll patients in the study.

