## 5 ANALYSIS SETS/POPULATIONS

### 5.1 FULL ANALYSIS SET

#### **Full Analysis Set 1 – Primary population**

Full Analysis Set 1 (FAS1) includes all patients who meet eligibility (inclusion/exclusion) criteria and with a radionuclide bone scintigraphy and/or SPECT performed with 99mTc-DPD/99mTc-PYP/99mTc-HMDP.

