### 6.3 OTHER ENDPOINTS

#### Primary endpoint

Patients with cardiac fixation at the radionuclide bone scintigraphy and/or SPECT performed with 99mTc-DPD or 99mTc-PYP or 99mTc-HMDP will be defined as patients with a cardiac retention of grade 1, grade 2 or grade 3.

Patients without cardiac fixation at the radionuclide bone scintigraphy performed and/or SPECT with 99mTc-DPD or 99mTc-PYP or 99mTc-HMDP will be defined as patients with a cardiac retention of grade 0.

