## 8. Sensitivity analyses

### 1) Impact of protocol amendment 2 - Use of SPECT

The prevalence of patients with cardiac fixation at the radionuclide bone scintigraphy and/or Single Photon Emission Computed Tomography (SPECT) performed with 99mTc-DPD or 99mTc-PYP or 99mTc-HMDP\* among patients with (left ventricular hypertrophy) LVH from undiagnosed etiology will be calculated in patients included before protocol amendment and in patients included after protocol amendment (Amendment 2 – Date: 11-Feb-2020). The percentage and its 95% CI will be provided.

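### Patients may enrol after the scan that supplies the primary endpoint, an exclusion footnote conflicts with this, and no analysis separates them from patients scanned after consent

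*Protocol*

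**What the plan says.** Protocol 9.2.5, inclusion e, accepts patients who "Plan to undergo or recently underwent radionuclide bone scintigraphy and/or SPECT with any of the following radio labelled tracers". The abstract and SAP 2.1 repeat it. None of them defines how recent the scan must be or requires consent before the result is read.

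Under SAP 6.3 (Primary endpoint), patients with cardiac fixation "will be defined as patients with a cardiac retention of grade 1, grade 2 or grade 3". For an already-scanned patient, the grade comes from that same scan.

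The footnote to exclusion a (Protocol 9.2.5, repeated in SAP 2.1) counts as a prior TTR diagnosis "any patient already diagnosed by any of the following: cardiac fixation at the bone scintigraphy", among other routes.

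FAS1 "includes all patients who meet eligibility (inclusion/exclusion) criteria and with a radionuclide bone scintigraphy and/or SPECT performed" (SAP 5.1), so both enrolment routes share one denominator. The only sensitivity analysis of the primary prevalence is the Amendment 2 comparison, in which it "will be calculated in patients included before protocol amendment and in patients included after protocol amendment". The SAP 5.3 subgroups are ATTRv and ATTRwt.

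The protocol does contain safeguards. Section 9.2.2 requires every eligible patient to be invited and a non-inclusion register to be completed. Section 9.9.2 concedes that "Voluntary or involuntary selection of patients in a study by investigators is inevitable", then says that systematic attempts to enrol can limit this bias. The variable list in 9.3 includes "Patient informed consent date", "Patient scintigraphy date" and the SPECT date.

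**The concern.** A patient with a planned scan consents before the endpoint exists. A patient scanned earlier may be approached, and may consent or decline, when the endpoint is already known. If approach, consent or eligibility then depends on the grade, the sample is selected on its own outcome.

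The primary result is a single proportion, with no comparator in which such a bias could cancel. The Wilson interval covers sampling error only, so the distortion would not show in the reported precision.

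The exclusion footnote adds to the problem. Applied literally, it makes eligibility depend on the result among already-scanned patients. Because FAS1 is defined by meeting the eligibility criteria, the reading adopted decides both who is enrolled and who is counted.

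**Working it through.** **Inputs from the documents.** Prevalence p = 10%, N = 1500, two-sided 95% interval, stated precision ±1.5 points (Protocol 9.5). The protocol gives the 10% for ATTR-CM but attaches it to the primary objective, so it is used here in the same way. The interval method is Wilson (SAP 8.1).

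**Inputs assumed, because the documents give neither.** f is the share of enrolled patients already scanned with a known result. r is the chance that a known positive is enrolled relative to a known negative. Underlying prevalence is taken as 10% in both routes.

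**Step 1: the plan's own figure.** 1.96 × √(0.10 × 0.90 / 1500) = 1.52 points. Wilson also gives 1.52 (8.58% to 11.62%). The stated ±1.5 reproduces.

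**Step 2: prevalence within the already-scanned group** = r·p / (r·p + 1 − p).
- r = 0: 0%
- r = 0.5: 0.05 / 0.95 = 5.3%
- r = 1: 10%
- r = 1.5: 0.15 / 1.05 = 14.3%
- r = 2: 0.20 / 1.10 = 18.2%

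r = 0 is the literal reading of the footnote.

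**Step 3: expected pooled estimate** = (1 − f) × 10% + f × (step 2).

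| f | r = 0 | r = 0.5 | r = 1 | r = 1.5 | r = 2 |
|---|---|---|---|---|---|
| 10% | 9.0% | 9.5% | 10.0% | 10.4% | 10.8% |
| 25% | 7.5% | 8.8% | 10.0% | 11.1% | 12.0% |
| 50% | 5.0% | 7.6% | 10.0% | 12.1% | 14.1% |

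**Step 4: share at which the bias equals the planned half-width.** f = 1.52 / |step 2 − 10|. For r = 0, 1.52 / 10 = 15%. For r = 2, 1.52 / 8.18 = 19%. For r = 0.5 and r = 1.5 the shares are 32% and 35%, so milder selection needs about a third of the sample to be already scanned.

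**Step 5: coverage of the nominal 95% Wilson interval at f = 25%, N = 1500 (exact binomial).** About 7% at r = 0 and about 26% at r = 2.

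**Step 6: can the SAP as written show this?** The Amendment 2 comparison divides patients by calendar date and is aimed at the introduction of SPECT. Either period may contain both enrolment routes, so the comparison does not isolate patients scanned before consent. Nothing else in the SAP uses the order of scan and consent.

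**The case against.** The strongest objection concerns direction. A reader might infer that sites would favour known positives and that the prevalence is therefore inflated. The documents do not support this: the exclusion footnote, taken at its word, bars known positives and would pull the estimate down. Neither direction can be assumed, and the range has to include r = 0.

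A reader might also infer that every already-scanned patient was enrolled with the result known. Inclusion e says only that the scan was done. Protocol 9.2.2 describes the scan and its reading as following the enrolment visit, and 9.3 lists no date of reading or disclosure. Scan before consent is thus a proxy for a known result.

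Size is open as well. At f = 25%, r = 0.5 and r = 1.5 give errors of −1.2 and +1.1 points, both inside the stated 1.5.

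The invite-all rule and the non-inclusion register are genuine safeguards, and 9.9.2 acknowledges patient selection in general terms. But 9.9.2 does not mention selection on a known result, and the SAP plans no analysis of the register. These points limit what can be said about direction and size. They leave standing that enrolment after the result is permitted, that two criteria pull against each other, and that the analysis cannot show the effect.

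**Conclusion.** The plan permits enrolment after the primary endpoint is known, the exclusion footnote conflicts with that permission for known positives, and FAS1 pools these patients with those scanned after consent. The primary prevalence is therefore open to selection on its own outcome.

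Whether bias occurred, and which way, cannot be settled from the documents. Under the assumptions above, the expected estimate for a true 10% runs from 9.0% to 10.8% if a tenth of patients were already scanned with a known result, and from 5.0% to 14.1% if half were. The bias matches the planned precision at a share of about 15% (r = 0) or 19% (r = 2), and is nil at r = 1. Both f and r are assumptions: the dates already collected would show approximately the first, while a comparison by scan timing would bear on the second without proving it.

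**What to change.** 1. **Reconcile the criteria.** The sponsor should reconcile inclusion e with the footnote to exclusion a and state how already-scanned positives were handled at enrolment and in FAS1. Without this, a low prevalence among patients scanned before consent could simply reflect the exclusion rule.

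2. **Add a sensitivity analysis to SAP 8.2.** From the consent, scintigraphy and SPECT dates, classify each FAS1 patient as scanned before consent or scanned on or after consent. Report the primary prevalence with its Wilson 95% interval in each group beside the pooled FAS1 figure. Tabulate the scan-to-consent interval and summarise the non-inclusion register.

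3. **Fix its role in advance.** Prespecify the scan-on-or-after-consent estimate as a sensitivity estimate free of selection on that scan's result, though not of referral selection. Pooled FAS1 remains the headline figure. It should not be replaced depending on whether the two groups happen to differ.

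The cost is one derived variable, one table and a register summary, with no new e-CRF data. The subset is less precise: at an illustrative n = 750 and 10%, 1.96 × √(0.09 / 750) is about ±2.1 points. A difference between the groups may also reflect case mix, site or calendar period, and the report should say so.

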## 2. Exclusion Criteria:

- a. Etiological diagnosis explaining the LVH prior to patient inclusion (eg, Sarcomeric HCM, Myeloma, Fabry disease, Sarcoidosis, any type of amyloidosis [AA, AL, TTR\*\*]).
- b. Severe aortic stenosis defined as aortic valve area (AVA) <1.0 cm^2.

*\*\* TTR diagnosis at exclusion criteria: Direct relative (siblings or parents) of a carrier with a known hereditary mutation in the TTR gene or any patient already diagnosed by any of the following: cardiac fixation at the bone scintigraphy, TR mutation at the genetic testing, biopsy with amyloidosis (positive red congo) and positive TTR staining.*

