### 2. Exclusion Criteria:

- a. Etiological diagnosis explaining the LVH prior to patient inclusion (eg, Sarcomeric HCM, Myeloma, Fabry disease, Sarcoidosis, any type of amyloidosis [AA, AL, TTR])
- b. Severe aortic stenosis defined as aortic valve area (AVA)  $< 1.0$  cm^2

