#### Secondary endpoints

##### 1. Presence of Transthyretin amyloid (ATTR) or patients with suspicion of MGUS / Light Chain Amyloidosis (AL)

- Patients with grade 2 or 3 at scintigraphy will be considered “Cardiac amyloidosis patients”
  - Patients with grade 2 or 3 at scintigraphy without monoclonal protein abnormalities will be considered patients with **ATTR amyloidosis**
  - Patients with grade 2 or 3 at scintigraphy with monoclonal protein abnormalities will be considered of the population of **patients with suspicion of MGUS or AL amyloidosis**
- Patients with grade 1 at scintigraphy will be considered as “**undetermined**”

Monoclonal protein abnormalities are defined as patients with positive IFE (Immunofixation electrophoresis) (serum and urine) or with abnormal FLC (free light chain) ratio:

	eGFR			
	>60	45-<60	30-<45	<30
Abnormal FLC ratio	≥1.65	≥1.92	≥2.06	≥2.17
Normal FLC ratio	<1.65	<1.92	<2.06	<2.17

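### The eligibility footnote counts cardiac fixation on bone scintigraphy as an excluding TTR diagnosis and does not exempt the recent scan that inclusion criterion e accepts, so the primary prevalence could be biased downward

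*Protocol*

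**What the plan says.** Protocol 9.2.5, inclusion criterion e, admits patients who "Plan to undergo or recently underwent radionuclide bone scintigraphy and/or SPECT with any of the following radio labelled tracers". It sets no time window for a recent scan and no condition on its result.

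Exclusion criterion a in the same section removes patients with an "Etiological diagnosis explaining the LVH prior to patient inclusion", and its examples include TTR amyloidosis. The footnote to that example defines a TTR diagnosis. Besides direct relatives of mutation carriers, it covers "any patient already diagnosed by any of the following: cardiac fixation at the bone scintigraphy", with a mutation on genetic testing and a positive biopsy as the other routes. SAP 2.1 repeats both criteria and the footnote. The abstract (Protocol 4) gives exclusion a without the footnote. The footnote names bone scintigraphy only; criterion e covers SPECT as well.

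SAP 5.1 states that FAS1, the primary population, "includes all patients who meet eligibility (inclusion/exclusion) criteria". SAP 6.3 says that patients with cardiac fixation "will be defined as patients with a cardiac retention of grade 1, grade 2 or grade 3". The finding that the footnote lists as a diagnosis is therefore also the primary outcome.

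**The concern.** A patient scanned shortly before enrolment, with a known grade 1, 2 or 3 result, meets criterion e. On a literal reading the same patient is excluded by criterion a, because fixation is one of the listed ways to be already diagnosed. A patient scanned at the same time with grade 0 meets criterion e and is not excluded. Entry to the denominator would then depend on the outcome.

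The result would be a downward bias in the single prevalence that the study exists to estimate, and a larger sample would not reduce it. If some sites read the footnote literally and others did not, the size of the bias would vary by site. This differs from the general patient-selection bias acknowledged in Protocol 9.9.2, where the remedy offered is systematic attempts to enrol. Here a site that excluded the positive patient would be following the written criterion.

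**Working it through.** **The plan's own figure.** Protocol 9.5 takes a prevalence of 10%, N = 1500 and a two-sided 95% interval, and states a precision of ±1.5 points. The half-width is 1.96 × √(p(1 − p)/N) = 1.96 × √(0.10 × 0.90/1500) = 0.0152, or 1.5 points, so the figure reproduces. The Wilson interval named in SAP 8.1 gives 8.6% to 11.6% for 150/1500, with the same half-width. The milestones in the abstract (Protocol 4) allow data collection to end once 1000 patients are screened. At N = 1000 the half-width is 1.96 × √(0.09/1000) = 0.0186, or 1.9 points.

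**Model of a literal reading.** Three inputs are needed, and the documents give none of them:
- p, the true prevalence of grade 1 to 3 fixation. The planning 10% is for ATTR-CM, so 20% and 30% are shown as an assumed range.
- h, the share of otherwise eligible patients whose scan result was known before inclusion. Protocol 9.2.2 describes the scan after the enrolment visit, so h may be small.
- s, the share of those known positives who are excluded.

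Assume that prevalence is the same whether or not the result was already known. Among all candidates, a fraction p·s·h is removed, all of it positive. Hence

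p_obs = p(1 − sh)/(1 − psh).

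Example with p = 10%, h = 25%, s = 1: of 1500 candidates, 150 are positive and 37.5 are removed, so p_obs = 112.5/1462.5 = 7.7%.

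| p | s | h = 10% | h = 25% | h = 50% |
|---|---|---|---|---|
| 10% | 1 | 9.1% | 7.7% | 5.3% |
| 20% | 1 | 18.4% | 15.8% | 11.1% |
| 30% | 1 | 27.8% | 24.3% | 17.6% |
| 10% | 0.5 | 9.5% | 8.9% | 7.7% |

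**Where the bias equals the 95% half-width.** With q = p − half-width, solving for h gives h = (p − q)/(s·p(1 − q)).
- p = 10%, s = 1, N = 1500: 0.0152/(0.10 × 0.9152) = 0.166, about 17%.
- p = 10%, s = 1, N = 1000: 0.0186/(0.10 × 0.9814 − 0.10 × 0.0628) = 0.0186/(0.10 × 0.9186) = 0.202, about 20%.
- p = 10%, s = 0.5: twice these, about 33% and 40%.
- p = 20%, s = 1 (half-widths 2.0 and 2.5 points): about 12% at N = 1500 and 15% at N = 1000.
- p = 30%, s = 1 (half-widths 2.3 and 2.8 points): about 11% and 13%.

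**The other reading.** If the footnote means only a diagnosis made before, and separately from, the qualifying scan, then s = 0 and p_obs = p for every h. The bias is zero.

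**The case against.** The best answer is that being already diagnosed means more than having a recent positive scan. Much of the documents' text supports this:
- Protocol 7 reports 68% specificity of any uptake for cardiac ATTR. It reserves 100% specificity for grade 2 or 3 uptake without a monoclonal protein, so a positive scan before that work-up is not plainly an etiological diagnosis.
- In SAP 6.3, "Patients with grade 1 at scintigraphy will be considered as" undetermined, not as ATTR.
- The note to criterion e lists all four grades without restriction, and SAP 5.1 defines FAS2 as the FAS1 patients with grade 1 to 3, so positive patients are expected to be eligible.
- Protocol 9.2.2 places the scan after the enrolment visit.
- The inclusion variables in Protocol 9.3 contain "AL, AA or any other amyloidosis" but no fixation item.
- A literal reading would leave criterion e admitting almost only negatives among patients with known results, which defeats the primary objective.

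All of this stands as evidence of intent. None of it states the rule for a patient scanned before inclusion, and a site could still apply the footnote as written. The flow chart, e-CRF, completion guidelines and non-inclusion register may settle the matter, but they were not available.

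A reader might infer that the criteria do remove recent positives and that the reported prevalence is therefore too low. The documents do not support that: nothing shows that any site applied the literal reading, and h, s and p are all unknown. A reader might also infer that comparing patients scanned before and after consent would reveal the problem. It would not do so reliably. Literal exclusion lowers the prevalence among those scanned before consent, while selective enrolment of known positives raises it, and the two may cancel.

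**Conclusion.** The gap in the text is real. Criterion e and the footnote overlap on patients with a recent positive scan, the overlap is on the primary outcome, and no available passage resolves it in either document. The direction of any bias from literal exclusion is downward. Its size is unknown: zero under the likely intent, and larger than the sampling error at p = 10% only if roughly 17% to 20% or more of candidates had a known result and every positive among them was excluded. Mixed site practice raises that threshold; a higher true prevalence lowers it. These figures are illustrations on assumed inputs, not estimates for this study. Low to moderate severity: the effect may be nil, but the clarification is nearly free and protects the primary estimate.

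**What to change.** 1. Reconcile criterion e with the footnote in Protocol 9.2.5 and SAP 2.1. State that the index scintigraphy or SPECT, meaning the scan that meets criterion e, does not count as a prior diagnosis whatever its grade. State also how fixation on an earlier SPECT alone is treated.
2. Derive FAS1 so that no enrolled patient leaves it because of the index result, and keep full FAS1 as the primary set.
3. Report reasons for exclusion from FAS1 by grade. SAP Table 15.1.1 already counts these patients by grade, but the shell shows no reasons. If the non-inclusion register records reasons, report how many patients were not included because of a recent positive scan.
4. Optionally, show the primary prevalence and grade counts by scan date before versus on or after consent. Label this descriptive: scan date is only a proxy for when the result was known, case mix and site may differ, and similar prevalences would not prove absence of bias. Since the footnote names only scintigraphy, SPECT-only patients are best shown separately.

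The cost is one sentence in each document, reasons added to one table, and at most one further table from dates already collected (Protocol 9.3). The optional split has wider intervals: if a quarter of patients were scanned before consent, 38/375 gives a Wilson interval of 7.5% to 13.6% and 112/1125 gives 8.3% to 11.8%.

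Data collection was planned to end in June 2022 and SAP version 2 is dated 06-Jul-2022. If enrolment is complete, new wording cannot recover patients who were turned away, and items 2 and 3 become the working remedy.
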